6.6. Prior and Concomitant Medication

Prior medications and concomitant medications will be coded using the WHO Drug Dictionary. Number and percentage of participants in the efficacy evaluable population for each prior and concomitant medications will be summarized by WHO drug class and WHO drug PT.

The number and percentage of participants with concomitant medications of phosphate binder will be summarized by WHO drug class and WHO drug term as follows:

- Phosphate binder includes but is not limited to the following terms: sevelamer, calcium acetate, calcium carbonate, lanthanum, ferric citrate, nicotinamide, tenapanor, aluminum hydroxyide, calcium citrate, and sucroferric oxyhydroxide.

7. EFFICACY

[Appendix C](#) provides a list of data displays.

7.1. Efficacy Hypotheses

Not applicable.

7.2. Analysis of the Primary Efficacy Parameter

7.2.1. Primary Efficacy Analysis

The primary endpoint of the study is the proportion of participants who achieve a BOR of CR as determined by investigator assessment according to the response criteria for myeloid/lymphoid neoplasms with FGFR1 rearrangement in [Appendix A](#). This analysis will be based on the efficacy evaluable population. Participants who do not have sufficient baseline or on-study response assessment information to be adequately assessed for response status will be included in the denominators in the calculation of CR rate. The 95% CI for the proportion of participants with CR will be estimated using the Clopper-Pearson method.

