6. STUDY ASSESSMENTS

All study assessments will be performed as indicated in the schedule of assessments (see [Table 4](#)), and all laboratory assessments will be performed as indicated in [Table 5](#). [Table 6](#) presents a summary of clinical laboratory analytes to be assessed. The order of assessments is suggested by the order of mention within the schedule. See Section [7](#) for instructions on each assessment. Further details of study procedures and assessments can be found in the study reference manual.

See [Appendix F](#) for COVID-19-related guidance.

Table 4: Study Assessments

Procedure	Protocol Section	Screening	Treatment				EOT	Follow-Up			Notes		
			Cycle 1		Cycle 2+*			Safety	Disease Status**	Survival			
			Day 1 (-28 to -1)	Day 8 (± 3 days)	Day 15 (± 3 days)	Day 1 (± 3 days)		EOT + 30 (+5) days	See Section 6.4.2	Every 12 (+2) weeks			
MLN w/FGFR1 rearrangement documentation	7.1	X									*See Section 6.2.1 for long-term treatment schedule. **Including post-transplant follow-up.		
Contact IRT	7.2	X	X			X*	X				*Assess for up-titration (Section 5.4.4)		
Informed consent	7.1	X											
Eye examination (slit lamp, visual acuity, funduscopic examination, OCT)	7.5.5	X				X*	X				*Every 3 cycles starting with Cycle 3 or as clinically indicated.		
Review inclusion and exclusion criteria	6.1	X	X										
Demography and medical history	7.3	X											
Prior/concomitant medications	7.4	X	X	X	X	X	X	X					
Physical examination/body weight, height	7.5.2	X*	X	X	X	X	X	X			*Comprehensive examination at screening only.		
Vital signs	7.5.3	X	X	X	X	X	X	X					
12-lead ECG	7.5.4	X	X*	X*	X	X**	X	X			*Timed triplicate ECG (separated by 2-5 minutes) performed at predose, 1 hour postdose, and 2 hours postdose. **After 12 months on treatment, ECG to be done every 3 cycles or more often if clinically indicated.		
ECOG status	7.7.1	X	X	X	X	X	X	X					
MPN-SAF/ EORTC QLQ-C30	7.7.2	X				X*	X				*Every 3 cycles starting with Cycle 3 for at least 12 months from the start of treatment (C1D1).		
Review AEs	7.5.1	X	X	X	X	X	X	X					

Table 4: Study Assessments (Continued)

Procedure	Protocol Section	Screening	Treatment				EOT	Follow-Up			Notes	
			Cycle 1		Cycle 2+*			Safety	Disease Status**	Survival		
			Days -28 to -1	Day 1	Day 8 (± 3 days)	Day 15 (± 3 days)	Day 1 (± 3 days)					
EFFICACY ASSESSMENTS (Appendix E)												

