Bone marrow examination (core biopsy and aspiration)	7.6, 7.9.4	X*				X**	X		X***		*Within 6 weeks before enrollment. **See Section 7.6 for assessment frequency. ***In subjects who do not discontinue due to progressive disease, including subjects in post-transplant follow-up.	
Lymph node/EMD biopsy (optional)	7.6	X*				X*					*In subjects who present with lymphadenopathy or other EMD, biopsy is recommended at baseline and at the time of progression.	
Cytogenetic analysis	7.6	X				X*	X		X**		*See Section 7.6 for assessment frequency. **In subjects who do not discontinue due to progressive disease, including subjects in post-transplant follow-up.	
EMD assessment by PET-CT or CT scan	7.6	X			X*	X*	X*		X*		See Section 7.6 for assessment frequency. *If baseline assessment is positive for EMD.	
Survival status	6.4.3									X		

CT = computed tomography; PET = positron emission tomography.

Table 5: Laboratory Assessments

	Protocol Section	Screening	Treatment				EOT	Safety Follow-Up 30 days from EOT (+5 days)	Notes			
			Cycle 1									
			Day 1	Day 8 (± 3 Days)	Day 15 (± 3 Days)							
LOCAL LABORATORY												
Serum chemistries	7.5.6	X	X*	X	X	X**	X	X	*May be performed within 3 days of the first dose. **Assess for up-titration (Section 5.4.4).			
Hematology	7.5.6	X	X*	X	X	X	X	X**	*May be performed within 3 days of the first dose. **Including subjects in post-transplant follow-up.			
Lipid panel	7.5.6		X									
Endocrine	7.5.6	X	X			X	X					
Coagulation panel	7.5.6	X				X*	X		*Every 3 cycles starting with Cycle 3.			
Hepatitis screening	7.5.6.2	X										
Urinalysis	7.5.6	X				X*			*Every 3 cycles starting with Cycle 3			
Pregnancy test	7.5.6.1	X (Serum)	X*			X*	X*		*Urine pregnancy test allowed; Day 1 of each cycle (see Section 6.2.1 for long-term treatment details).			

Table 5: Laboratory Assessments (Continued)

Protocol Section	Screening	Treatment				Cycles 2+ EOT	Safety Follow-Up 30 days from EOT (+5 days)	Notes			
		Cycle 1									
		Day 1	Day 8 (± 3 Days)	Day 15 (± 3 Days)							
CENTRAL LABORATORY											
Bone marrow (aspirate, core, and peripheral blood smear)	7.6, 7.9.4	X				X*	X	*See Table 7 for assessment frequency.			
PK	7.8		X	X				Samples will be drawn at predose and 1, 2, and 4-12 hours postdose (4 samples total on each day).			
Correlative plasma sample	7.9.3		X		X	X*		*C2D1, C4D1, C8D1, then at the times of scheduled bone marrow sampling (see Table 7 for assessment frequency).			

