6.4.2.1. Post-Transplant Follow-Up

Subjects who have a successful HSCT should be followed for disease status post-transplant as well. Data from standard-of-care transplant assessments (eg, pretransplant preparation, conditioning regimen, donor, type, GVHD, relapse, transplant-related mortality, graft failure, peripheral blood smears, CBCs, differentials, bone marrow biopsy, bone marrow aspirate, cytogenetics) will be collected from these subjects until they have withdrawn from the study.

Post-transplant subjects should return to the investigative site for bone marrow exams, hematology blood work and, if applicable, imaging studies, as noted in Section [7.6](#).

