7.6.2. Bone Marrow Exams and Cytogenetics

Bone marrow examinations are an integral part of assessing subject response to treatment and will be collected according to the following parameters:

- The components of a complete bone marrow exam will consist of a core biopsy, marrow aspirate, and associated peripheral blood smear slides. Every reasonable effort should be made to perform a complete exam at each disease assessment, however instances where all exam components cannot be obtained (eg, aspirate is a dry tap or core biopsy is contraindicated) will not be considered protocol deviations.
- Bone marrow exams will be conducted according to the schedule provided in [Table 7](#) and continue until disease progression or the completion of the disease follow-up period (Section [6.4.2](#)).
- Subjects who successfully bridge to HSCT should continue to have bone marrow examinations and peripheral blood smears, CBCs, and differentials assessed according to local standard of care.

Table 7: Bone Marrow Exam Schedule

Study Phase	Exam Frequency
Screening (baseline)	
• Obtained within 6 weeks of enrollment (Cycle 1 Day 1).
Treatment	
• After 6 (\pm 1) weeks (just prior to Cycle 3) and then every 9 (\pm 1) weeks from Cycle 1 Day 1 for the first 12 months (eg, until Week 51/Cycle 18) on treatment.• After 12 months on treatment, every 18 (\pm 1) weeks for subjects who have not yet achieved CCyR or every 52 (\pm 2) weeks for subjects who have a confirmed CCyR. If progression is suspected in peripheral blood, a bone marrow biopsy and bone marrow aspirate should be conducted as an unscheduled visit as soon as possible.
Disease status follow-up	
• Subjects who enter the disease status follow-up for reasons other than to bridge to transplant may continue to have disease assessments according to the schedule above.• Subjects who bridge to transplant should have bone marrow examinations and peripheral blood smears, CBCs, and differentials at 1 to 3 months and 6 months post-transplant and then as per local standard of care. Slides from these exams will be forwarded to the central pathologist for review.

Flow cytometry is not a required component of the bone marrow exam; however, if it is performed, the results should be captured in the eCRF.

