9.4. Statistical Analyses

9.4.1. Efficacy Analyses

9.4.1.1. Primary Efficacy Analyses

The primary endpoint of this study is the proportion of subjects who achieved a BOR of CR as determined by investigator assessment according to the response criteria for myeloid/lymphoid neoplasms with FGFR1 rearrangement (see [Appendix E](#)). This analysis will be based on the efficacy evaluable population. Subjects who do not have sufficient baseline or on-study response assessment information to be adequately assessed for response status will be included in the denominators in the calculation of overall response rate. The 95% CI for the proportion of subjects with CR will be estimated using the Clopper-Pearson method.

The proportion of subjects who achieved a BOR of CR will also be analyzed based on the PP population as a sensitivity analysis.

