9.4.1.2. Secondary Efficacy Analyses

Secondary efficacy analyses will be conducted for the efficacy evaluable population.

The proportion of subjects who achieve response, defined as BOR of CR or PR, as determined by investigator assessment according to the response criteria listed in [Appendix E](#), will be estimated with its 95% CI.

The proportion of subjects who achieve BOR of CCyR as assessed by local analysis and investigator evaluation will be estimated with its 95% CI.

The proportion of subjects who achieve BOR of PCyR as assessed by local analysis and investigator evaluation will be estimated with its 95% confidence interval.

Duration of CR, defined as the time from first assessment of CR to the earlier of disease progression or death due to any cause. Subjects without disease progression or death at the time of analysis will be censored at the date of last response assessment before the cutoff date.

Duration of CR will be analyzed by the Kaplan-Meier method.

Duration of response, defined as the time from first assessment of CR or PR to the earlier of disease progression or death due to any cause. Subjects without disease progression or death at the time of analysis will be censored at the date of last response assessment before the cutoff date. Duration of response will be analyzed by the Kaplan-Meier method.

Progression-free survival is defined as the time from the first date of taking study drug until the date of disease progression, as measured by response criteria or until death due to any cause, whichever is earlier. Subjects who are still alive without experiencing disease progression at the time of analysis will be censored at the date of the last response assessment before the cut-off date. Progression-free survival data will be analyzed by the Kaplan-Meier method.

Overall survival is defined as the time from the first day of taking study drug until death due to any cause. Subjects without death observed at the time of the analysis will be censored at last date known to be alive. Overall survival will be analyzed by the Kaplan-Meier method.

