22. Incorporation of administrative changes. Other regulatory guidance and administrative changes have been incorporated throughout the Protocol and are noted in the redline version of the amendment.

Amendment 5 (02 JUL 2020)

Overall Rationale for the Amendment:

The main purpose of this amendment is to include updated language for comprehensive eye examination, per FDA feedback. Other modifications have been made to include a long-term treatment visit schedule option for subjects with stable response, to update the Protocol with program-level standard language and post-transplant follow-up, and to provide additional language clarifications.

- 1. Synopsis; Section 6, Study Assessments (Table 4: Study Assessments; Table 5: Laboratory Assessments); Section 6.2.1, Long-Term Treatment Visit Schedule; Section 7.5.6.1, Pregnancy Testing**

Description of change: Language was added to provide subjects who have been on study treatment for more than 78 weeks (18 months), have had a stable clinical and cytogenetic response and manageable adverse events the option to extend study visit frequency to every 3 cycles (9 weeks).

Rationale for change: To ease subject's long-term study visit burden.

- 2. Section 5.4.2, Criteria and Procedures for Dose Interruptions and Adjustments of Study Drug; Section 5.4.3, Management of Hyperphosphatemia; Section 5.4.5, Criteria for Permanent Discontinuation of Study Drug**

Description of change: Added pemigatinib program standard language.

Rationale for change: To conform to pemigatinib development standard language.

- 3. Section 6, Study Assessments (Table 6: Required Analytes); Section 7.5.6.2, Hepatitis Screening Tests**

Description of change: Clarified hepatitis screening requirements.

Rationale for change: To clarify Protocol.

- 4. Section 6, Study Assessments (Table 4: Study Assessments); Section 6.4.2.1, Post-Transplant Follow-Up; Section 7.6.2, Bone Marrow Exams and Cytogenetics (Table 7: Bone Marrow Exam Schedule)**

Description of change: Added language regarding standard of care data to be collected following subjects who successfully bridge to transplant. Added language relative to post-transplant efficacy assessments, including bone marrow examinations.

Rationale for change: Post-transplant status data added per FDA request.

Post-transplant bone marrow examinations added at the end of the post-transplant follow-up period to allow for a final comprehensive efficacy analysis.

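### No end is set on the assessments that feed best overall response, so a CR first seen after stem cell transplant is not excluded from the primary CR rate

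*SAP*

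**What the plan says.** **Primary rate.** SAP 7.2.1 reads: "The primary endpoint of the study is the proportion of participants who achieve a BOR of CR as determined by investigator assessment". Protocol 9.4.1.1 matches the SAP: "The primary endpoint of this study is the proportion of subjects who achieved a BOR of CR as determined by investigator assessment". Neither section gives a first or last date for the assessments used. BOR is only spelled out in the abbreviation lists, and the response criteria (Protocol Appendix E, SAP Appendix A) set no window. SAP 7.2.1 does mention on-study assessments, but only to keep non-assessable participants in the denominator.

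**Assessments after transplant.** Protocol 6.4.2.1 says: "Subjects who have a successful HSCT should be followed for disease status post-transplant as well". It brings these subjects back to the site for marrow, hematology and, where relevant, imaging. Table 7 in Protocol 7.6.2 adds: "Subjects who bridge to transplant should have bone marrow examinations and peripheral blood smears, CBCs, and differentials at 1 to 3 months", and again at 6 months. Table 4 puts the marrow and cytogenetic rows under the heading "EFFICACY ASSESSMENTS (Appendix E" and says who has them in disease status follow-up: "In subjects who do not discontinue due to progressive disease, including subjects in post-transplant follow-up". SAP 2.1 keeps the SAP in force for later Protocol amendments.

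**Durations.** SAP 7.3 censors duration of CR, duration of response and PFS at the last response assessment before new cancer therapy or transplant. Protocol 9.4.1.2 has no transplant rule; those without progression or death are "censored at the date of last response assessment before the cutoff date".

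**Central review and transplant outcomes.** SAP 7.4 repeats the BOR-based rates by central review without a window, and reports transplant outcomes separately for participants transplanted without progression.

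**The concern.** The rate and the durations follow different rules about transplant. A CR that first appears after conditioning and transplant cannot be separated from the effect of those treatments, yet nothing keeps it out of the primary numerator. The CR-or-PR, CCyR and PCyR rates in SAP 7.3 and their central-review versions in SAP 7.4 have the same gap, and it extends to responses first seen after other new cancer therapy.

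Two things are at stake. Two programmers could both follow the SAP and report different CR rates. And a participant could count as a complete responder without a usable duration of CR.

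**Working it through.** **1. The plan's own figure.** Inputs from Protocol 9.2 and SAP 3.3: n about 46, true CR rate 35%, lower limit of the 95% CI above 15%, 10% lost, probability above 80%. The interval is Clopper-Pearson (SAP 7.2.1). Take the smallest count r whose lower limit exceeds 15%, then P(X ≥ r) for X ~ Binomial(n, 0.35).
- n = 46: 12/46 has lower limit 14.3% and 13/46 has 16.0%, so r = 13; P = 86.8%.
- After 10% loss, 46 × 0.9 = 41.4. n = 41: r = 12 (lower limit 16.1%; 11/41 gives 14.2%), P = 82.4%. n = 42: r = 12, P = 85.0%.

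The stated figure reproduces when lost participants are removed from the denominator. A pre-transplant window leaves these design figures unchanged.

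**2. Rate and duration side by side.** Take a participant transplanted before progression whose first CR comes afterwards.
- CR rate (SAP 7.2.1): no rule excludes the CR.
- Duration of CR (SAP 7.3): the start is the first CR assessment, after transplant. Without a later event counting, the censoring date is the last response assessment before transplant.
- So censoring date < transplant date < start date, and censoring date − start date is negative whatever the actual dates.

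**3. Size of one reclassified CR.** 1/46 = 2.2 points. At n = 47, the number treated by 16 APR 2023 (Protocol 1.3.2), 1/47 = 2.1 points. SAP 5.3.1 restricts the FDA efficacy set to participants with prior systemic therapy. Its size is not given; at an assumed 41 or 36, one CR is 2.4 or 2.8 points.
- Near the assumed rate: 16/46 = 34.8% (95% CI 21.4 to 50.2); 15/46 = 32.6% (19.5 to 48.0).
- Near the sizing target: 13/46 = 28.3% (16.0 to 43.5); 12/46 = 26.1% (14.3 to 41.1).

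**4. Range for an assumed number.** Let k of 46 be CRs first seen after transplant and counted, and let the other 46 − k have a true CR rate of 15%. The chance that the lower limit exceeds 15% is P(X ≥ 13 − k), X ~ Binomial(46 − k, 0.15): 1.5% (k = 0), 3.0% (k = 1), 5.7% (k = 2), 10.1% (k = 3), 16.9% (k = 4). The values of k are assumptions.

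**5. Confirmation.** Footnote d to the response criteria requires resolved counts to persist over at least 8 weeks. If baseline counts are abnormal and first normal at Cycle 1 Day 8, then 8 + 56 = Day 64, which is Cycle 4 Day 1 (1 + 3 × 21), ignoring visit windows. After a transplant before then, scheduled confirmation could come only from post-transplant counts. Footnote c similarly requires at least two marrow assessments to confirm improvement in fibrosis. Neither document says whether post-transplant results may complete either confirmation.

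**The case against.** **Intent is visible.** The SAP applies one transplant cut to three endpoints and reports transplant outcomes apart, and Protocol 7.6 frames the assessment as response to treatment. This points towards the same cut for the rates. It stands as evidence of intent, and it would be too strong to say that intent cannot be inferred. It is still not a derivation rule. Protocol 6.4.2 does end disease-status collection at new antineoplastic therapy, but that governs collection, and 6.4.2.1 resumes it after transplant.

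**Unseen documents may settle it.** The Protocol does not say that an Appendix E response category is recorded after transplant. The case report forms, table shells and committee charter are not available here. This stands: they may limit the practical ambiguity.

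**Stronger readings that do not hold.**
- A reader might infer that the SAP authors overlooked a known exam schedule. The SAP is dated 24 FEB 2021; the amendment log places the 1-to-3-month and 6-month exams in Amendment 6, of 13 JUL 2023. The Amendment 5 entry says only: "Post-transplant bone marrow examinations added at the end of the post-transplant follow-up period to allow for a final comprehensive efficacy analysis". So some post-transplant exam was in view, but not demonstrably this schedule. The SAP now covers it through section 2.1.
- A reader might take SAP 7.4 as planning for participants whose first CR follows transplant. It covers everyone transplanted without progression, including those already in CR. Its example of more than 10 participants triggers a summary; it does not forecast a number.

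**Confirmation is a corner case.** It needs abnormal baseline counts and an early transplant (footnote d) or baseline fibrosis (footnote c), and unscheduled visits are allowed. Requiring all confirmation before transplant could also reclassify someone who normalised on pemigatinib. That stands, so the plan should state a choice, but this review does not impose one.

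**Conclusion.** The gap is real and should be closed before the final analysis. The plan as written does not exclude a CR first seen after transplant from the primary rate, and counting one would conflict with the SAP's own duration rule. This follows from the text and needs no assumption about numbers.

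The size is unknown. The documents give no count of first CRs after transplant, and it may be zero. Each is worth 2.2 points at n = 46. One could move the lower limit across 15%, but 15% is the sizing target: SAP 7.1 states no efficacy hypothesis, so crossing it is not a formal decision. The documents do not support a claim that the CR rate will be materially inflated.

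**What to change.** Change the SAP only, in 7.2.1, 7.3 and 7.4:
- State that BOR (CR, PR, CCyR, PCyR; investigator and central review) is the best response from first dose to the earliest of disease progression, new cancer therapy, stem cell transplant or data cutoff.
- List responses first seen after transplant separately.
- Show the CR rate without the cut as a sensitivity analysis.
- State whether post-transplant counts or marrow may complete the footnote c and d confirmation; if any participant is affected, show the CR rate both ways.
- Date the change and record it in SAP section 9. The trial is open-label and 47 participants had been treated by 16 APR 2023, so the date and the sensitivity row guard against the appearance of a data-driven choice.

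The cost is a few sentences, a listing flag and one or two table rows. No new data are needed: SAP Appendix C already plans listings of response, bone marrow, post-therapy and stem cell transplant. A Protocol amendment, which Protocol 10.1 would send to health authorities and ethics committees, is not needed; SAP 9.1 already records one change to a Protocol-defined analysis. The downside is that the reported CR rate may be slightly lower.
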